6. STUDY LIMITATIONS

Since participation in the registry will be voluntary, registry participants may not be representative of the overall SLE pregnant population. The most appropriate external comparator data and published literature available may be used to assist the interpretation of pregnancy registry outcome data. Care will be taken during data interpretation since external data may differ from registry data with regard to factors other than belimumab exposure. These factors may include the population under study, SLE clinical characteristics and disease severity, medications used to treat SLE, concomitant medical conditions, data source or collection methods, etc. thus potentially confounding any reported associations. Detailed data on such potential confounders may not be available, especially for any identified external cohorts, and hence it may be difficult to employ adjustment methodologies in the analysis.

The primary study population of belimumab exposed participants will include pure prospective pregnancies (i.e. (a) enrollee did not know at the time of enrollment whether the fetus had a malformation, and (b) no prenatal testing was completed prior to enrollment). Sensitivity analyses will be conducted with traditional prospective pregnancies comprised of women who enroll in the registry prior to the end of pregnancy (live birth, fetal loss, etc), regardless of known normal or abnormal prenatal test results.

While the primary analysis population in this registry will be limited to pure prospective reports, some belimumab-exposed pregnancies will be reported to the registry after the pregnancy ended (i.e. live birth, fetal loss, etc or retrospective reports) or following notification of an abnormal prenatal test result (included in traditional prospective

reports). In general, reports made to the registry after the pregnancy has ended and/or notification of an abnormal prenatal test result are biased toward reporting of the severe and unusual cases and are not reflective of the general experience with the medication. Moreover, information about the total number of exposed persons is not known. Therefore, rates of outcomes cannot be calculated from these data. However, a series of reported birth defects can be evaluated to detect patterns of specific birth defects and can assist with identification of potential early signals of therapy risks.

As reporting of pregnancies will be totally voluntary, it is possible that even in pure prospective reported cases, potential bias could exist. For example, high-risk pregnancies or low-risk pregnancies may be more likely to be reported.

Those pregnancies that have reached EDD, but for which pregnancy outcome information was unobtainable after multiple attempts, will be considered lost to follow-up. It is possible that outcomes among pregnancies lost to follow-up could differ from those with documented outcomes. Because of differences in follow-up procedures across countries and individual reporting patterns, it is currently not possible to assess with any certainty what impact the potential biases the losses to follow-up may have on the analysis. However, efforts to compare some of the characteristics of each cohort may be conducted in an attempt to address this potential source of bias.

Fetal losses for which no birth defects have been reported may introduce misclassification bias. The percentage of these pregnancies consisting of potentially normal outcomes or birth defects is unknown. The data collection form will attempt to obtain information on birth defects detected at the time of the outcome. However, the reporting physician may not know the condition of the miscarried fetus.

7. STUDY MANAGEMENT

7.1. Ethical Approval

Institutional Review Board (IRB)/Ethics Committee (EC) approval or notification will be obtained or performed, respectively, in countries where this is required.

7.2. Informed Consent Process

Participant informed consent is required for participation in this pregnancy registry. Under applicable regulations in the US and several European countries, signed informed consent may be waived and verbal informed consent allowed.

Adults

Eligible adults who wish to participate in the registry will be asked to provide informed consent. Signed informed consent will be obtained in countries where it is required by local laws and regulations. In certain countries, the registry may qualify for verbal informed consent or waiver of documentation of signed informed consent (obtained by the process described below).

To facilitate verbal informed consent, registry coordinating center staff or the participant's HCP will review the Participant Information Sheet Consent Form with the pregnant woman (candidate registry participant) by telephone. The candidate registry participant is given an opportunity to ask questions and have them answered. If the candidate participant still wishes to participate in the registry, she provides verbal consent. This verbal consent is documented by registry coordinating center staff who forwards the registry participant a letter stating that she has provided verbal consent for registry participation together with a copy of the Participant Information Sheet/Consent form reviewed with the participant.

Minors

Minors are defined as individuals who have not attained the legal age for consenting to treatments, procedures, or clinical investigations under applicable law in the countries in which the registry is being conducted. Belimumab is not approved for treatment of minors. However, if a minor requests to participate in the registry, the registry will permit this participation, if all eligibility criteria are met and on acquisition of assent from the minor and signed written consent from the parent or guardian. Written consent from both parents and/or guardians will be obtained in the US states and other countries, if this is required by local laws and regulations.

At the initial screening with potential participants, the registry associate will obtain consent to collect basic information about the individual, such as age and state or country of residence to determine whether the individual is a minor and to ensure that applicable local laws and regulations are followed.

7.2.1. Waiver of Signed Informed Consent for Registry participants in the US

Eligible adults in the US who wish to participate in the registry will be asked to provide verbal informed consent. The following US regulations indicate that waiver of signed informed consent should be appropriate for this registry in the US.

As stated in the US Code of Federal Regulations (CFR) 21 CFR 56.109 (and additionally in 45 CFR 46.117(c)(2)):

"(c) An IRB shall require documentation of informed consent in accordance with 50.27 of this chapter, except as follows:

(1) The IRB may, for some or all subjects, waive the requirement that the subject, or the subjects legally authorized representative, sign a written consent form if it finds that the research presents no more than minimal risk of harm to subjects and involves no procedures for which written consent is normally required outside the research context; or

(2) The IRB may, for some or all subjects, find that the requirements in 50.24 of this chapter for an exception from informed consent for emergency research are met.

(d) In cases where the documentation requirement is waived under paragraph (c)(1) of this section, the IRB may require the investigator to provide subjects with a written statement regarding the research."

The research will involve no more than minimal risk to the subjects. This will be an observational study that involves no experimental intervention and poses no possibility of physical harm. The only potential risk will be a breach of confidentiality, and the registry will have well-established procedures in place to prevent any such breach of confidentiality. Extensive safeguards will be in place to ensure that participants' privacy is protected:

- An adequate plan is provided to protect the identifiers from improper use and disclosure (see Section 7.3).
- An adequate plan is provided to remove the identifiers at the earliest opportunity.
- Adequate assurances are provided that the protected health information will not be reused or disclosed to any other person or entity.

The research will involve no procedures for which written consent is normally required outside the research context. Enrollment in this observational study will be strictly voluntary. The schedule of participant visits and all treatment regimens will be at the complete discretion of the treating HCP. Data submitted to the registry will be limited to data routinely collected and documented in the participant's medical record.

7.2.2. Release of Participant Medical Information to the Registry

In order to collect data from the participant's health care providers and her newborn's pediatric health care provider, registry participants in all countries must complete medical release forms for each clinician who will report data to the registry.

7.2.2.1. Exemption of HIPAA Authorization for Registry Participants in the US

As a post-marketing safety reporting activity, this registry meets the criteria outlined below and should therefore be exempt from the US HIPAA Authorization as specified in 45 CFR 164.512 (b)(iii) which states:

"(iii) A person subject to the jurisdiction of the Food and Drug Administration (FDA) with respect to an FDA-regulated product or activity for which that person has responsibility, for the purpose of activities related to the quality, safety or effectiveness of such FDA-regulated product or activity. Such purposes include:

- a. To collect or report adverse events (or similar activities with respect to food or dietary supplements), product defects or problems (including problems with the use or labeling of a product), or biological product deviations;
- b. To track FDA-regulated products;
- c. To enable product recalls, repairs, or replacement, or lookback (including locating and notifying individuals who have received

products that have been recalled, withdrawn, or are the subject of lookback); or

- d. To conduct post marketing surveillance;"
- e. To further clarify this issue, an article published by the Pregnancy Labeling Task Force, US FDA, states:

"...the HIPAA Privacy Rule specifically permits the disclosure of protected health information by covered entities such as physicians or hospitals for public health purposes related to the quality, effectiveness and safety of FDA-regulated products to both the manufacturers and directly to the FDA. This includes collecting or reporting adverse events, tracking FDA-regulated products and conducting post-marketing surveillance to comply with requirements or at the direction of the FDA." [Kennedy, 2004.]

7.2.2.2. Release of Medical Information to the Registry Outside of the US

For all countries outside of the US, the registry will comply with local laws and regulations to facilitate release of participant medical information to the registry.

7.3. Participant Confidentiality

Each participant's identity will be known only to the third-party contractor (Registry Coordinating Center), the registry site, enrolling individual (i.e., participant or HCP), and relevant HCPs (i.e. belimumab prescriber, obstetrician, pediatrician). The registry will assign participant and infant identification numbers, which will be used to identify registry participants and their infant offspring. The dataset used in each analysis of data from the registry will contain coded registry participant identifiers only for both the pregnant mothers and infants.

Regulatory authorities, or GSK approved auditors, may inspect the registry data files which may include personal identifier information of registry participants.

7.4. Reporting of Adverse Drug Events

An adverse event (AE) is any untoward medical occurrence in a patient or clinical investigation subject administered a pharmaceutical product, which does not necessarily have a causal relationship with the treatment. An AE can therefore be any unfavourable and unintended sign (including an abnormal laboratory finding), symptom or disease (new or exacerbated) temporally associated with the use of a Medicinal Product. For a marketed Medicinal Product, this can also include failure to produce expected benefits (i.e. lack of efficacy, with or without an adverse event), and adverse events associated with circumstances of Overdose whether accidental or intentional, Medication Errors, Abuse or effects of drug withdrawal, or Misuse.

For both belimumab exposed and unexposed participants, serious adverse events (SAEs) will be defined as those adverse events that result in death, are life-threatening; require inpatient hospitalization or prolongation of existing hospitalization; result in persistent or significant disability/incapacity; or is a congenital anomaly/birth defect. In addition,

based upon appropriate medical judgment, important medical events that may not be immediately life-threatening or result in death or hospitalization, but may jeopardize the patient or may require intervention to prevent one of the other outcomes listed above is considered a SAE. Adverse events (AEs), if reported, will be recorded on registry data collection tools as part of registry data collection (and considered 'solicited' for regulatory reporting purposes).

If an AE is considered serious by the reporter, a SAE Report Form will be completed. All SAEs will be entered into the registry database and forwarded to GSK within 1 business day of registry notification. In addition, any other adverse pregnancy outcomes will also be reported to GSK within 1 business day of registry notification.

GSK will then forward all AE information to regulatory agencies as required by applicable regulations. The registry will follow industry guidance [FDA, 2002; EMEA, 2005] for regulatory reporting of adverse pregnancy outcomes and serious infections experienced by the infants.

7.5. Study Closure/Uninterpretability of Results

In accordance with industry guidance [FDA, 2002], the registry could consider discontinuation at any of the following times:

- Sufficient information has accumulated to meet the scientific objectives of the registry
- Other methods of gathering appropriate information become achievable or are deemed preferable
- The feasibility of collecting sufficient information diminishes to unacceptable levels because of low exposure rates, poor enrollment, or losses to follow-up

Prior to discontinuing this registry, the regulatory authorities will be consulted, as appropriate.

7.6. Study Milestones

This registry is intended to be available for initiation of recruitment in participating countries from the time of launch following acquisition of market authorization. Recruitment will continue until the criteria described in Section 5 have been achieved. Study close-out and final reporting activities will be initiated on completion of the pregnancy outcome and infant follow-up on the last participant in the registry.

7.7. Study Sponsor

This study will be conducted by GSK. GSK will sponsor the study in all countries. GSK will lead on the operational conduct of the registry worldwide working with the Contract Research Organization.

7.8. Central Registry Sites/Principal Investigators

Each country participating in the registry will have a central registry site and principal investigator who will be responsible for the following tasks:

- Submitting protocol for IRB/EC approval
- Promoting the registry among interested physicians and medical societies and assisting in developing and nurturing a national network of physicians who will report data to the registry
- Assisting in registry awareness activities
- Coordinating and facilitating enrollment of eligible participants into the registry and collecting follow-up data
- Assisting in assessment of case report form data submitted from reporters and in resolution of data queries
- Transferring data to the Registry Coordinating Center

Any HCP caring for eligible pregnant women may participate in the registry. Interested HCPs should contact the central registry site or Registry Coordinating Center to participate.

7.9. Registry Coordinating Center

The Registry Coordinating Center will be responsible for the overall daily management of the registry and facilitating all data collection and management activities. The Registry Coordinating Center will be responsible for the following tasks:

- Assisting the sites in submitting the registry protocol for IRB and EC approval
- Assisting the sites in promoting the registry among interested physicians and medical societies, and assisting in developing and nurturing a national network of physicians who will report data to the registry
- Assisting in all other registry awareness activities
- Assisting the sites in facilitating enrollment of eligible participants and collecting follow-up data
- Assessing case report form data submitted from reporters and resolving data queries
- Entering, managing, and analyzing data
- Updating the registry interim and final reports
- Overseeing the activities of the sites
- Ensuring that all case reports of serious adverse events and all adverse pregnancy outcomes are forwarded to GSK within 1 business day of registry notification for regulatory reporting requirements and entered into the registry database

- Ensuring that all follow-up data, that are attainable from HCPs, on serious adverse events and all adverse pregnancy outcomes are forwarded to GSK within 1 business day of receipt and entered into the registry database
- Contributing to the scheduling and planning of the registry Scientific Advisory Committee (SAC) meetings and participation in SAC meetings

7.10. Scientific Advisory Committee

The SAC will consist of selected global experts such as those specializing in the treatment of SLE, maternal and fetal medicine, teratology, epidemiology/biostatistics, pediatrics, and representatives from GSK (clinical, statistics, epidemiology). The SAC will be responsible for supervising the data collection and analysis; however, these activities will be performed by an independent external group that is experienced in the conduct and operations of registries. The SAC will be expected to meet at least annually to perform an independent review of the data collected, including review and classification of reported birth defects, and to carry out any actions required, including review and interpretation of interim data analyses and reports and publications of registry data. The SAC may meet on ad hoc occasions if indicated. In addition to the above activities, the SAC may design and implement strategies to heighten awareness of the registry.

An expert in teratology will be included in the SAC and will act as the birth defect evaluator for the registry. His/her responsibilities will include the review, evaluation, and classification of reports of birth defects. Additionally, the birth defect evaluator will provide an opinion regarding the possible temporal association of the belimumab exposure or other SLE treatment exposure to the development of observed defects.

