4.3.2. Birth Defects

The registry will define and code birth defects with criteria specified by Centers for Disease Control and Prevention (CDC)'s Metropolitan Atlanta Congenital Defects Program (MACDP) (Birth Defects and Genetic Diseases Branch 6 – Digit Code for Reportable Congenital Anomalies, Version 08/07). Newborn and infant conditions that are not necessarily considered birth defects appear in the Exclusion List for the MACDP. These conditions may be included under certain circumstances by CDC criteria and will be considered "conditional defects" in the registry.

The registry will define a defect as any major structural or chromosomal defect or combination of 2 or more of the conditional defects in live-born infants, stillbirths, or fetal losses of any gestational age (including outcomes prior to 20 weeks' gestation or weighing <500 g). This definition is consistent with, but not restricted to, the CDC MACDP definition. Clusters of conditional defects (as defined by CDC MACDP) and data from aborted fetuses of less than 20 weeks' gestation, when available, will be included to increase sensitivity of monitoring. The MACDP includes conditional defects only if in the presence of a major structural defect. In contrast, this registry will consider reports of 2 or more conditional defects as a birth defect case, to increase potential signal generation and to capture instances where a combination of conditional defects might constitute a major birth defect or syndrome.

The registry will conform to the CDC MACDP guidelines in disqualifying birth defects if those findings are present in infants born at less than 36 weeks of gestation and are attributable to prematurity itself, such as patent ductus arteriosus, patent foramen ovale, or inguinal hernias. The CDC MACDP classification includes chromosomal defects. Though these defects are not likely to contribute to a risk for a drug exposure, the registry will include these birth defects to maintain this consistency with the CDC MACDP.

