Live-born infants with only transient or infectious conditions or with biochemical abnormalities (e.g., jaundice) will be classified as being without reported birth defects unless there is a possibility that the condition reflects an unrecognized birth defect. Detected and reported transient or infectious conditions or biochemical abnormalities in infants without reported birth defects and defects that are excluded by the CDC guidelines will be reviewed and noted in an appendix in the registry reports.

Because this registry will be conducted in North America and Europe at a minimum, the registry will use the European Surveillance of Congenital Anomalies (EUROCAT) in addition to the US-based CDC MACDP in subgroup-analyses and/or with specific SLE comparator cohorts, if data are available or applicable.

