Small for Gestational Age (SGA)	Defined as an infant whose birth weight is less than the 10^{th} percentile for the gestational age. The registry will utilize the sex specific international growth reference standards from the INTERGROWTH-21 st group (Villar, 2014) for those born at \geq 33 weeks GA and also those endorsed by ACOG (Alexander, 1996) for all infants of all gestational ages.
Spontaneous miscarriage	Fetal death or expulsion of products of conception prior to 20 weeks' gestation. Terminology may include missed abortion, blighted ovum, incomplete abortion, and inevitable abortion.
Stillbirth	A fetal death occurring 20 weeks' gestation or greater, or if the gestational age is not available, weighing 500 g or more.
Temporality assessment	The determination of the probable association or non- association of the timing of the maternal exposure in pregnancy relative to the probable timing of organogenesis of a defect.
Term birth	An infant at outcome \geq 37 weeks' gestational age, or if gestational age is not available, weighing \geq 2,500 g.

Term	Registry Definition
Thrombocytopenia	A decreased number of platelets in the blood associated with an increased risk of bleeding. A peripheral blood platelet count greater than 150,000/ mm ³ is considered normal, 50,000 - 150,000/mm ³ is consistent with mild to moderate thrombocytopenia, and less than 50,000/mm ³ is consistent with severe thrombocytopenia.
Traditional prospective report	Traditional prospective reports of pregnancy will include all women who enroll in the registry before the end of pregnancy (live birth, fetal loss, etc), regardless of known normal or abnormal prenatal test results.

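### One evaluator both classifies birth defects and judges their timing against treatment, with no step that fixes case status before exposure timing is seen

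*Protocol*

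**What the plan says.** Birth defects are the only primary endpoint (Protocol Section 2.2). Section 7.10 places a teratology expert on the Scientific Advisory Committee (SAC) as birth defect evaluator: "His/her responsibilities will include the review, evaluation, and classification of reports of birth defects". It then adds that "the birth defect evaluator will provide an opinion regarding the possible temporal association of the belimumab exposure or other SLE treatment exposure" to the defects observed. The Glossary (Section 9) defines temporality assessment through "the timing of the maternal exposure in pregnancy relative to the probable timing of organogenesis of a defect", so the opinion cannot be given without exposure dates.

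Section 7.10 also expects the SAC as a whole to "perform an independent review of the data collected, including review and classification of reported birth defects". Its members include sponsor staff from clinical, statistics and epidemiology. No recusal from classification is stated.

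Section 4.3.2 sets the case rules. Coding follows MACDP criteria, and two or more conditional defects make a case. Two clauses call for an opinion:
- Findings before 36 weeks are disqualified if they "are attributable to prematurity itself, such as patent ductus arteriosus, patent foramen ovale, or inguinal hernias".
- Infants with only transient, infectious or biochemical conditions count as unaffected "unless there is a possibility that the condition reflects an unrecognized birth defect".

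**The concern.** When one person decides whether a finding is a case and also judges whether its timing fits the drug, the second judgement can leak into the first. A borderline finding may be accepted more readily after first-trimester dosing than after dosing only before conception or late in pregnancy. The protocol reports outcomes by earliest trimester of exposure because organogenesis falls in the first trimester (Section 4.8.2.2). Classification made with timing in view could therefore build part of the expected gradient into the data.

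The unexposed SABLE pregnancies raise a related issue. Sections 4.8.5 and 7.11 use them to interpret signals: an anomaly seen in both groups may point away from belimumab. That reading needs the same case threshold in both groups.

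Calling the committee's review independent is also hard to square with unrestricted sponsor membership when the committee classifies the primary endpoint.

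**Working it through.** **1. What needs judgement and what does not**

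| Decision | Governing text | Room for opinion |
|---|---|---|
| Clear major structural or chromosomal defect | MACDP codes (4.3.2) | Little |
| Cluster of conditional defects | Conditional = on the MACDP Exclusion List (Glossary); two or more = case (4.3.2) | Little; it is a count |
| Finding before 36 weeks due to prematurity? | 4.3.2, following MACDP guidelines | Yes; attribution |
| Transient condition reflecting an unrecognized defect? | 4.3.2 | Yes; a possibility suffices |

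The prematurity question may arise fairly often. Section 1.1 cites about 40% preterm delivery in SLE. Section 4.3.1 defines preterm as under 37 weeks, so the share born under 36 weeks is smaller and is not given.

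**2. Where exposure varies**

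- Within the primary population every case is exposed (4.8.2, 4.8.2.1), but timing differs: before conception or by trimester (4.4, 4.8.1, 4.8.2.2).
- Between groups, the exposed/unexposed label differs, but no formal comparison is planned (4.8.3).
- Against MACDP, only the registry's cases could be classified with belimumab timing in view.

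The first two are the routes by which knowledge of exposure could act most directly.

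**3. The plan's own precision figure**

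Inputs (Section 5): 350 live births, prevalence 2.78%, exact interval 1.32% to 5.09%. The expected count is 0.0278 × 350 = 9.73. Clopper-Pearson limits are Beta(0.025; x, n − x + 1) and Beta(0.975; x + 1, n − x). With x = 9.73 and n = 350 they are 1.325% and 5.093%, which reproduces the stated interval.

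**4. Weight of one classification (illustration)**

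One infant at n = 350 changes the estimate by 1/350 = 0.286 percentage points.

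| Cases / 350 | Estimate | Exact 95% CI |
|---|---|---|
| 9 | 2.57% | 1.18% to 4.83% |
| 10 | 2.86% | 1.38% to 5.19% |
| 11 | 3.14% | 1.58% to 5.55% |

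Across the live-birth range in Section 5, the step is 1/380 = 0.26 to 1/311 = 0.32 points.

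The 350 sits within a range derived from 500 traditional prospective enrolments (500 × 0.83 × 0.75 = 311; 500 × 0.95 × 0.80 = 380). The primary population is the pure prospective subset, whose size is not given. If it held a fraction f of the 350, the step would be 0.286/f points: 0.57 at f = 0.5 and 1.14 at f = 0.25. Both fractions are assumptions.

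**The case against.** The strongest reply is that Section 7.10 assigns roles and does not say that exposure is shown during classification. It lists classification first and the temporality opinion second. Redaction and form design could sit in a committee charter that is not shown. This has force: a reader might infer that the exposure record is always in view when case status is decided, and the text does not establish that. What stands is that the protocol gives both tasks to one person and contains no step separating them.

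Several further points hold and narrow the concern:
- Exposure timing is not a case criterion in Section 4.3.2, Section 4.8.2.2 or the Glossary. Chromosomal defects are kept as cases although the protocol thinks them unlikely to bear on drug risk. Discounting a defect because of dosing dates would breach the definition.
- Transient conditions and CDC-excluded defects are noted in a report appendix (4.3.2), and single minor defects are listed (4.8.2.2). Many downgraded findings would therefore remain visible.
- The evaluator is not described as a sponsor employee, and no text expressly gives sponsor members a vote on classification. Section 7.10 has an independent external group perform data collection and analysis, but it is not said to classify defects.
- The registry definition is openly wider than MACDP's, and Sections 4.8.3.2 and 6 warn about differences from external data.

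A reader might also infer that the headline rate, or its comparison with MACDP, is materially biased. The documents do not support that. The primary population is all exposed, so the exposure label cannot vary within it. The number of borderline cases is unknown. Even a three-case shift from 10/350, an invented size, gives 7/350 = 2.00% (0.81% to 4.08%) or 13/350 = 3.71% (1.99% to 6.27%), and both intervals contain 2.78%.

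**Conclusion.** The point holds as a design weakness of limited reach. The protocol joins classification of the primary endpoint and the temporality opinion in one evaluator without a lock between them. It also gives classification to a committee, described as reviewing independently, that has sponsor members.

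The exposure-sensitive decisions are the prematurity attribution and the transient-condition clause. The places most open to influence are the trimester strata and the descriptive exposed/unexposed reading of signals. Any effect on the overall rate against MACDP is less certain, and its direction cannot be told.

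The step of 0.29 points per infant measures sensitivity and does not estimate bias. It rests on 350 live births and about ten cases, and it is larger in the pure prospective population by an unknown factor. The conclusion assumes that no unseen charter already masks exposure; if one does, Section 7.10 need only refer to it.

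**What to change.** Amend Section 7.10 so that the existing evaluator works in two steps:
1. Decide and lock case or non-case and the MACDP code from a narrative with exposure group, drug names and dosing dates removed, for exposed and unexposed reports alike.
2. Receive the exposure data and give the temporality opinion. Any later change of classification is logged with its reason.

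State in the same section that sponsor representatives on the SAC do not vote on case classification. Reporting to the sponsor within one business day (Section 7.4) and ongoing signal review (Section 7.11) continue unchanged.

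The cost is redaction of a small number of narratives by the coordinating center, a two-part review form and a minor delay per case; no extra reader is needed. Masking will be imperfect because most participants are exposed and the evaluator knows it is a belimumab registry. Exposure timing and the exposed/unexposed label can still be withheld, and those matter most here.
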